7. TREATMENT PLAN

7.1. Nintedanib Dosage and Administration

Research participants for this study will initiate treatment with 200mg of oral nintedanib twice per day. The capsules should be swallowed whole (unopened, uncrushed) with a glass of approximately 8 oz. /240 mL of water. Since subjects will be taking oral nintedanib twice daily, the dose interval should be every 12 hours at the same time every day, usually in the morning and the evening after food intake.

In case of a missed dose the subjects should not replace that dose, but proceed to the next scheduled dose when it is due. Each study cycle length is 28 days.

In the event of a treatment delay at the scheduled Day 1 of a cycle, Day 1 of that cycle will be delayed until study treatment is re-started. This may cause a cycle to extend to longer than 28 days. Day 1 will be defined as the day the treatment is re-started.

For dose selection and modifications, see Section 8.

7.1.1 Nintedanib (BIBF 1120) Drug Supply

Nintedanib capsules for oral administration are formulated as soft gelatin capsules in two dose strengths (100 mg or 150 mg) and is provided in 30 count bottle. 100 mg capsules are peach, opaque, oblong, soft capsules imprinted in black with the BI company symbol and "100". 150 mg capsules are brown, opaque, oblong, soft capsules imprinted in black with the BI company symbol "150". Nintedanib will be supplied by BI. To request nintedanib from Boehringer Ingelheim, IDS Pharmacy will complete the BI-provided Drug Supply Request Form. Drug inventory levels should be able to provide subjects with nintedanib for up to 4-8 weeks while waiting for additional ordered supplies. The LCI Investigational Drug Services Pharmacy will receive nintedanib capsules of 100mg; 150 mg dosage in study drug bottles containing 30 capsules each. The study drug bottles will have a label affixed containing study identification, product identification and quantity of capsules. Once the drug has been received, it must be kept in a secure, dry location. Study drug must be stored in study drug bottle at room temperature 25°C (77°F). Temperature excursions between 15° to 30°C (59° to 86°F) is permitted.

7.2. Treatment Compliance

Nintedanib will be dispensed to subjects with instructions to return study drug pill bottles to research staff. Study drug bottles will be returned to the dispensing pharmacy. Capsules will be counted by pharmacy staff or delegate and reported to the

applicable research designee. The number of capsules taken by the subject per cycle will be determined by these capsule counts.

The subject will be considered to be compliant with treatment if $\geq 75\%$ of doses were taken during any given cycle and overall, unless protocol treatment is withheld for toxicity.

Subject compliance with the treatment and protocol includes willingness to comply with all aspects of the protocol. At the discretion of the Sponsor-Investigator, a subject may be discontinued from protocol for non-compliance with follow-up visits or study drug.

7.3. Duration of Therapy

In the absence of treatment delays due to adverse event(s), treatment will continue until one of the following criteria applies:

- Disease progression
- Intercurrent illness that prevents further administration of treatment
- Unacceptable adverse event(s)
- Subject decides to withdraw study consent
- General or specific changes in the subject's condition render the subject unacceptable for further treatment in the judgment of the Investigator.

Note: In the event the criteria for the final analysis are met, and there are subjects who have not yet been discontinued from study treatment, they will continue to receive therapy beyond the date the criteria for the study final analysis are met and until one of the above criteria applies.

7.4. Drug Accountability

All study drugs will be stored at the investigational site in accordance with product labeling, Good Clinical Practice (GCP) and Good Manufacturing Practices (GMP) requirements and will be inaccessible to unauthorized personnel.

The study bottles will be returned to the pharmacy from which it was dispensed. Pharmacy or a designee will count the number of pills and communicate that to the applicable research designee.

An adequate record of receipt, distribution, and return or destruction of all study drugs must be kept in the form of a Drug Accountability Form. The Investigator, or

responsible party designated by the Investigator, will maintain a careful record of the inventory using the Drug Accountability Form.

7.5. Destruction

At the end of the study, unused and/or partially used supplies of nintedanib will be destroyed according to LCI IDS pharmacy policies.

8. NINTEDANIB INTERRUPTION

8.1. Criteria for Interruption of Treatment with Nintedanib

Treatment with nintedanib will be interrupted according to the criteria listed in Table 1.

In the event of a treatment delay at the time of Day 1 of a cycle, Day 1 of that cycle will be delayed until study treatment is re-started. This may cause a cycle to extend to longer than 28 days.

Table 1: Criteria for interrupting treatment with nintedanib due to an adverse event

If at least one criterion is met, nintedanib will be interrupted:
 
 nausea of CTCAE grade ≥ 3 despite supportive care vomiting of CTCAE grade ≥ 2 despite supportive care diarrhea of CTCAE grade ≥ 2 for more than 3 consecutive days despite supportive care AST and/or ALT elevations of $> 2.5 \times$ ULN in conjunction with bilirubin of $> 1.5 \times$ ULN AST and/or ALT elevations of $> 5 \times$ ULN other non-hematological adverse event of CTCAE grade ≥ 3 considered drug-related Neutropenia grade 3 or 4 and fever $> 38.5^{\circ}\text{C}$ Neutropenia CTCAE grade 4 for more than 7 days without fever Platelets $< 50,000\text{mm}^3$ with bleeding High blood pressure; SBP > 170 mm Hg, or DBP > 100 mm Hg Clinically significant bleeding, CTCAE grade 3 or 4, or grade 2 for 3 or more days
--

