8.2. Criteria to Restart Treatment with Nintedanib

A research participant is eligible to restart nintedanib if all criteria listed in Table 2 are met.

If a subject must interrupt intake of nintedanib due to an adverse event for more than 14 days, the decision to restart treatment with nintedanib needs to be discussed and agreed upon between the sponsor-investigator and the treating physician.

Table 2: Criteria to assess eligibility to restart nintedanib treatment

All criteria must be met in order to restart nintedanib, meaning AEs have to return to Grade 1 or baseline (exception is nausea- see below).
 
  nausea CTCAE grade ≤ 2  vomiting CTCAE grade ≤ 1  diarrhea CTCAE grade ≤ 1  AST and ALT $< 2.5 \times \text{ULN}$; bilirubin $< 1.5 \times \text{ULN}$  no other non-hematological adverse event grade CTCAE ≥ 3 which is considered drug-related  *Neutropenia CTCAE grade ≤ 1, without fever or equal to the subject's pre-therapy value at study enrolment  *Platelets CTCAE grade ≤ 1 or equal to the subject's pre-therapy value at study enrolment  Blood pressure SBP<150 mm Hg; DBP <90 mm Hg  Bleeding CTCAE grade 1 or less
--

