8.3. Dose Adjustments of Nintedanib

As initial measure for the management of side effects (see section 9), treatment with nintedanib should be temporarily interrupted until the specific adverse reaction has resolved to levels that allow continuation of therapy. Nintedanib treatment will be resumed at a reduced dose. Dose adjustments in 100 mg increments per day (i.e. a 50mg reduction per dosing) based on individual safety and tolerability are recommended as described in Table 1. In case of further persistence of the adverse reaction(s), i.e. if a subject does not tolerate 100 mg twice daily, treatment with nintedanib should be discontinued.

The following dose levels will be used in case dose adjustments are required for management of toxicity (see Table 3).

Table 3: Nintedanib dose levels – example for starting dose of 200mg twice daily

Dose-level:	0	-1	-2	-3
Dose:	2 x 200 mg/day	2 x 150 mg/day	2 x 100 mg/day	discontinue treatment

Of note:

If the dose of nintedanib had to be reduced due to toxicity, the subject will stay on the lower dose level for the entire time of administration.

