9. TREATMENT-RELATED ADVERSE EVENTS

9.1. Management of Adverse Events

Based on prior clinical studies with nintedanib, the sponsor investigator should anticipate that any or all of the following AEs could occur. The occurrence of AEs and SAEs should prompt immediate notification to appropriate agencies as outlined in Section 11.6-11.8.

As an initial measure for the management of side effects, treatment with nintedanib should be temporarily interrupted as outlined in Table 1 until the specific adverse reaction has resolved to levels that allow restarting of therapy. Nintedanib treatment may be resumed at a reduced dose as outlined in table 4. Dose adjustments in 100 mg steps per day (i.e. a 50 mg reduction per dosing) based on individual safety and tolerability are recommended as described in Table 4. In case of further persistence of the adverse reaction(s), i.e. if a subject does not tolerate 100 mg twice daily, treatment with nintedanib should be discontinued.

Table 4: Dose adjustments for Nintedanib

CTCAE* Adverse reaction	Dose adjustment
Diarrhea \geq grade 2 for more than 7 consecutive days despite anti- diarrheal treatment** OR diarrhea \geq grade 3 despite anti- diarrheal treatment**	1st episode Reduce dose from 200 mg twice daily to
Vomiting ** \geq grade 2 AND/OR Nausea \geq grade 3 despite anti-emetic treatment**	150 mg twice daily 2nd episode Reduce dose from 150 mg twice daily to
AST and/or ALT elevations of $> 2.5 \times$ ULN in conjunction with bilirubin of $> 1.5 \times$ ULN OR AST and/or ALT elevations of $> 5 \times$ ULN	100 mg twice daily 3rd episode Stop treatment
Other non-haematological or haematological adverse reaction of \geq grade 3	
Elevation of AST and/or ALT values to $> 3 \times$ ULN in conjunction with an increase of total bilirubin to $\geq 2 \times$ ULN and ALKP $< 2 \times$ ULN	Unless there is an alternative cause established, nintedanib should be permanently discontinued

*CTCAE- v4.03: Common Terminology Criteria for Adverse Events

** see also section 9.2.

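### Table 1 mandates no hold for treatment-refractory grade 3–4 diarrhea until a grade ≥2 course has lasted more than 3 days, although Table 4 makes it a dose-reduction trigger at any duration

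*Combined protocol and SAP*

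**What the plan says.** Table 1 in Section 8.1 is binding: "If at least one criterion is met, nintedanib will be interrupted". Its diarrhea line requires grade ≥2 "for more than 3 consecutive days despite supportive care". Nausea of grade ≥3 and vomiting of grade ≥2, each despite supportive care, are held with no duration condition. A residual line covers any "other non-hematological adverse event of CTCAE grade" 3 or higher that is considered drug-related.

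Table 2 in Section 8.2 governs restarts: "All criteria must be met in order to restart nintedanib, meaning AEs have to return to Grade 1 or baseline". For diarrhea that means grade ≤1.

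Section 8.3 gives interruption as the initial measure: "treatment with nintedanib should be temporarily interrupted until the specific adverse reaction has resolved to levels that allow continuation of therapy". Treatment then resumes at a reduced dose, with adjustments "based on individual safety and tolerability are recommended as described in Table 1". After a reduction for toxicity, "the subject will stay on the lower dose level for the entire time of administration".

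Table 4 in Section 9.1 lists two diarrhea triggers for a dose reduction: grade ≥2 for more than 7 consecutive days despite treatment, or at least "grade 3 despite anti- diarrheal treatment", the latter with no duration. Section 9.1 also says treatment should be interrupted, but by the Table 1 criteria. Section 9.2 says diarrhea may require interruption, reduction or discontinuation.

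**The concern.** The only rule that obliges a site to stop the drug for diarrhea is based on duration and has no severity override. Read literally, grade 2 diarrhea must be held on day 4, while grade 4 diarrhea on days 1 to 3 need not be. Yet the dose-reduction table regards grade ≥3 diarrhea under treatment as serious enough to act on at any duration, and a reduction is not reversed.

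This is a patient-safety point. Section 3 puts gastrointestinal events, diarrhea among them, first in its list of main risks. In the nintedanib monotherapy lung trial (Section 2.2.2), drug-related diarrhea was reported in 47.9%, between nausea (57.5%) and vomiting (42.5%), both of which have a hold without a duration condition. Exclusion criterion w lets subjects with chronic diarrhea enter if they tolerate anti-diarrheals. Treatment is oral and outpatient, and the day 8 and day 15 contacts may be by phone, so written thresholds carry weight.

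**Working it through.** The main check sets the lists side by side. Hematological events are left out; Table 1 sets narrower limits for those than Table 4 does.

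| Event | Table 1: must hold | Table 4: reduce dose |
|---|---|---|
| Nausea ≥3 despite treatment | yes | yes |
| Vomiting ≥2 despite treatment | yes | yes |
| AST/ALT >2.5× ULN with bilirubin >1.5× ULN | yes | yes |
| AST/ALT >5× ULN | yes | yes |
| Other non-hematological ≥3 | yes, if drug-related | yes |
| Diarrhea ≥2, prolonged | after >3 days | after >7 days |
| Diarrhea ≥3 despite treatment, any duration | **no line** | yes |

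Only the last row has a reduction trigger without a matching hold.

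Applying the rules to cases:

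- Grade 3 for 1 to 3 days despite loperamide: no Table 1 hold; Table 4 reduction criterion met. This is the gap.
- Grade 3 for more than 3 days: hold and reduction both met.
- Grade 3 arising after more than 3 days of grade 2: Table 1 is already met, so not in the gap.
- Grade 2 for 4 to 7 days: hold met, Table 4 reduction not met.

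**Exposure per episode.** The longest period without a mandated hold is 3 days × 2 doses = 6 doses.

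- At 200 mg BID: 6 × 200 = 1,200 mg.
- If the first reduction is applied immediately: 6 × 150 = 900 mg.
- In a second episode, reduced immediately: 6 × 100 = 600 mg.
- In a third episode Table 4 stops treatment.

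These are ceilings, because the diarrhea must first fail anti-diarrheal treatment.

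**Subjects affected.** The documents give neither a monotherapy rate of grade ≥3 diarrhea nor episode durations, so the number in the gap cannot be derived. For scale, any-grade diarrhea at the monotherapy rate would be 0.479 × 39 = 18.7 subjects. Three assumed figures for all grade ≥3 diarrhea, whatever its duration:

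- Excess over docetaxel alone from the Section 9.2 rates: (0.063 − 0.036) × 39 = 1.05.
- Excess from the Section 2.2.2 rates: (0.066 − 0.026) × 39 = 1.56.
- Monotherapy any-grade rate times the combination-arm share at grade ≥3: 43/276 = 0.156; 0.479 × 0.156 = 0.0746; 0.0746 × 39 = 2.9.

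All three borrow from a docetaxel-combination trial, and Section 9.2 notes that the diarrhea there was closely related in time to docetaxel. Only courses of 3 days or less lie wholly in the gap. On these assumptions the number is between 0 and about 3 of 39.

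**Cross-reference.** Section 8.3 points to Table 1 for dose adjustments, but Table 1 contains none. The near-identical sentence in Section 9.1 points to Table 4, which does contain them.

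**The case against.** The strongest defense is the workflow in Sections 8.3 and 9.1. Interruption is the initial measure, and the Table 4 doses are those at which treatment is resumed. A reader might infer from the mismatch that the protocol has subjects step down and keep dosing through active grade 3–4 diarrhea. The documents do not support that: the described order is interrupt, resolve, resume at a lower dose. What remains is that Section 8.3 says *should*, without a grade or duration, and Section 9.1 ties interruption back to Table 1, where the criterion is missing.

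A second defense is that the residual Table 1 line catches drug-related grade ≥3 diarrhea, since holding every unlisted grade 3 event but not grade 4 diarrhea is an unlikely intent. That may well be what was meant. But *other* follows a separate diarrhea line, and Tables 1, 2 and 4 all list diarrhea beside an *other* line. If sites can read it both ways, the text needs the edit. Section 7.3 also ends treatment for unacceptable adverse events, but that is permanent discontinuation, not a hold.

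Other stronger readings also fail:

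- The Table 4 reduction is not automatic at the first grade 3 stool count. It requires failure of anti-diarrheals and is a recommendation based on individual tolerability.
- Nausea and vomiting are not held from the first moment either, because those lines also require failure of supportive care.
- Section 2.3.2 does not show that a few days' exposure within an episode worsens diarrhea. It compares assigned doses of 150 mg and 250 mg BID, and it is unclear whether its grade 3–4 qualifier extends to diarrhea.
- A reader sent to Table 1 by Section 8.3 might reduce the dose after 4 to 7 days of grade 2 diarrhea, but Section 9.1 states the reference correctly and Table 4 is titled for dose adjustments. The slip is clerical.

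**Conclusion.** The mismatch is real, and it is one of mandatory wording. For grade 3–4 diarrhea despite treatment, in a grade ≥2 course of 3 days or less, no binding rule requires a hold; only *should* and *may* language does the work. This rests on reading *other* in Table 1 literally.

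The consequence is limited to the dose ceiling shown above, and 1,200 mg applies only if the Table 4 reduction has not yet been made. The figure of 0 to about 3 of 39 subjects is an illustration built partly on combination data, not an estimate. The two-stage decision rule, sample size and error rates are untouched. The change is worth making because it is a cheap safety clarification, not because the documents show that many subjects would be exposed.

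**What to change.** 1. Add to Table 1: *diarrhea of CTCAE grade ≥3 despite anti-diarrheal treatment, any duration*. Keep the grade 2 sequence as it is (hold after more than 3 days, reduce after more than 7). Table 2 then governs the restart, at the Table 4 dose.
2. As a clerical correction, cite Table 4 instead of Table 1 for dose adjustments in Section 8.3.

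Neither edit adds procedures or subjects. By Table 5 in Section 11.4.4, even a minor change needs the funder's prior approval. The clinical downside is an occasional extra hold of up to about 3 days per episode: a short course is back to grade ≤1 by then, and a longer one is already held from day 4. For a subject treated for six 28-day cycles (assumed for illustration), one such hold is 3/168 = 1.8% of the intended dose.

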8.2. Criteria to Restart Treatment with Nintedanib

A research participant is eligible to restart nintedanib if all criteria listed in Table 2 are met.

If a subject must interrupt intake of nintedanib due to an adverse event for more than 14 days, the decision to restart treatment with nintedanib needs to be discussed and agreed upon between the sponsor-investigator and the treating physician.

Table 2: Criteria to assess eligibility to restart nintedanib treatment

All criteria must be met in order to restart nintedanib, meaning AEs have to return to Grade 1 or baseline (exception is nausea- see below).
 
  nausea CTCAE grade ≤ 2  vomiting CTCAE grade ≤ 1  diarrhea CTCAE grade ≤ 1  AST and ALT $< 2.5 \times \text{ULN}$; bilirubin $< 1.5 \times \text{ULN}$  no other non-hematological adverse event grade CTCAE ≥ 3 which is considered drug-related  *Neutropenia CTCAE grade ≤ 1, without fever or equal to the subject's pre-therapy value at study enrolment  *Platelets CTCAE grade ≤ 1 or equal to the subject's pre-therapy value at study enrolment  Blood pressure SBP<150 mm Hg; DBP <90 mm Hg  Bleeding CTCAE grade 1 or less
--

8.3. Dose Adjustments of Nintedanib

As initial measure for the management of side effects (see section 9), treatment with nintedanib should be temporarily interrupted until the specific adverse reaction has resolved to levels that allow continuation of therapy. Nintedanib treatment will be resumed at a reduced dose. Dose adjustments in 100 mg increments per day (i.e. a 50mg reduction per dosing) based on individual safety and tolerability are recommended as described in Table 1. In case of further persistence of the adverse reaction(s), i.e. if a subject does not tolerate 100 mg twice daily, treatment with nintedanib should be discontinued.

The following dose levels will be used in case dose adjustments are required for management of toxicity (see Table 3).

Table 3: Nintedanib dose levels – example for starting dose of 200mg twice daily

Dose-level:	0	-1	-2	-3
Dose:	2 x 200 mg/day	2 x 150 mg/day	2 x 100 mg/day	discontinue treatment

Of note:

If the dose of nintedanib had to be reduced due to toxicity, the subject will stay on the lower dose level for the entire time of administration.

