F. Sample	Up to 39 subjects. Stage I: 28 evaluable subjects. If the study continues to Stage II: an additional 11 evaluable subjects
G. Inclusion Criteria	
 • Histologically confirmed stage IV appendiceal carcinoma • Failure of initial fluoropyrimidine-based chemotherapy. Failure is defined as progression on or within 6 months of therapy or intolerance of initial fluoropyrimidine-based chemotherapy • ECOG performance status score 0-2 • Measurable and/or evaluable, non-measurable disease according to RECIST 1.1 criteria
H. Dosage/ Dosage Form, Route, And Dose Regimen	Subjects will take oral nintedanib (200mg) twice daily. Dose reductions to 150mg and then 100mg twice daily as needed based on toxicity. Each cycle is 28 days.
I. Statistical Analysis	Disease control will be determined for each subject as a binary variable indicating whether or not the subject achieved a best overall response of CR, PR, or SD as determined by RECIST 1.1. Disease control rate will be estimated with the corresponding 95% Clopper-Pearson confidence interval. Objective response rate and 6-month PFS rate will be estimated with the corresponding 95% Clopper-Pearson confidence interval. Progression-free survival and overall survival rates will be estimated using Kaplan-Meier techniques. Multivariable regression models will be used to evaluate the impact of baseline subject and disease characteristics on outcomes. Incident rates for adverse events, SAEs, and deaths while on study therapy will be summarized.

SCHEMA

Endpoints

Primary: DCR

Secondary: OS, ORR, overall and 6 month PFS, safety/toxicity

Exploratory: Serum VEGF, hypertension, ascites VEGF, paracentesis

Statistical Plan

Single arm, two-stage design of 39 patients

LIST OF ABBREVIATIONS

β-HCG	β-human chorionic gonadotropin
γ-GT	γ-Glutamyl Transferase
5-HT ₃	5-Hydroxy-Tryptamin receptor 3
AE	Adverse event
AESI	Adverse event of special interest
ALKP	Alkaline phosphatase
ALT / ALT (SGPT)	Alanine aminotransferase / Alanine aminotransferase (serum glutamic pyruvic transaminase)
ANC	Absolute neutrophil count
AP	Alkaline Phosphatase
AST / AST (SGOT)	Aspartate aminotransferase / Aspartate aminotransferase (serum glutamic-oxaloacetic transaminase)
ATP	Adenosine triphosphate
bFGF	Basic fibroblast growth factor
BI	Boehringer Ingelheim
BID	Twice daily
BSA	Body surface area
BUN	Blood urea nitrogen
CHS	Carolinas HealthCare System
CI	Confidence interval
CK	Creatine kinase
CK-MB	Creatine kinase-MB

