9.2. Additional Precautions for Nintedanib

- *Diarrhea*
Diarrhea was the most frequently reported gastro-intestinal event and appeared in close temporal relationship with the administration of docetaxel in

the clinical trial LUME-Lung 1¹⁰. The majority of subjects had mild to moderate diarrhea. 6.3 % had diarrhea of grade ≥ 3 in combination treatment compared to 3.6 % treated with docetaxel alone. Diarrhea should be treated at first signs with adequate hydration and anti-diarrheal medicinal products, e.g. loperamide, and may require interruption, dose reduction or discontinuation of therapy with nintedanib.

- *Nausea and vomiting*

Nausea and vomiting, mostly of mild to moderate severity, were frequently reported gastrointestinal adverse events in the clinical trial LUME-Lung 1¹⁰. Interruption, dose reduction or discontinuation of therapy with nintedanib may be required despite appropriate supportive care. Supportive care for nausea and vomiting may include medicinal products with anti-emetic properties, e.g. glucocorticoids, anti-histamines or 5-HT₃ receptor antagonists and adequate hydration.

In the event of dehydration, administration of electrolytes and fluids is required. Plasma levels of electrolytes should be monitored, if relevant gastrointestinal adverse events occur.

- *Neutropenia and Sepsis*

A higher frequency of neutropenia of CTCAE grade ≥ 3 was observed in subjects treated with nintedanib in combination with docetaxel as compared to treatment with docetaxel alone in the clinical trial LUME-Lung 1¹⁰. Subsequent complications such as sepsis or febrile neutropenia have been observed.

Blood counts should be monitored during therapy, if nintedanib (BIBF 1120) is combined with a myelosuppressive agent.

- *Hepatic Function*

The safety and efficacy of nintedanib has not been studied in patients with moderate (Child Pugh B) or severe (Child Pugh C) hepatic impairment. Therefore, treatment with nintedanib is not recommended in such patients.

Administration of nintedanib was associated with an elevation of liver enzymes (ALT, AST, ALKP (alkaline phosphatase), and bilirubin), with a potentially higher risk for female patients.

These increases were reversible in the majority of cases and not associated with clinically manifest liver disorders. Hepatic transaminases, ALKP and

bilirubin levels are recommended to be closely monitored after start of therapy with nintedanib.

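### Sections 8.3 and 9.1 give different instructions on the nintedanib dose after a hold, and the Table 2 heading disagrees with its own fifth restart criterion

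*Combined protocol and SAP*

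**What the plan says.** Table 1 (Section 8.1) lists the events that require nintedanib to be held, Table 2 (Section 8.2) sets the conditions for restarting, and Sections 8.3 and 9.1 deal with the dose afterwards.

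**Section 8.3.** After the hold, "Nintedanib treatment will be resumed at a reduced dose". The next sentence says that steps of 50 mg per dose "based on individual safety and tolerability are recommended as described in Table 1". The sentence before Table 3 is conditional: "The following dose levels will be used in case dose adjustments are required for management of toxicity". Once the dose has been reduced for toxicity, "the subject will stay on the lower dose level for the entire time of administration".

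**Section 9.1.** A nearly identical paragraph reads "Nintedanib treatment may be resumed at a reduced dose as outlined in table 4", and its sentence on 50 mg steps cites Table 4 instead of Table 1. Table 4 holds the reduction triggers.

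**Elsewhere.** Item H of the Protocol Summary has "Dose reductions to 150mg and then 100mg twice daily as needed based on toxicity". Section 9.2 says that diarrhea "may require interruption, dose reduction or discontinuation of therapy with nintedanib".

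**Table 2.** The heading demands that all criteria be met, explains this as recovery of adverse events to grade 1 or baseline, and names nausea as the exception. The fifth criterion blocks restart only while another drug-related non-hematological event stands at grade 3 or higher.

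**The concern.** Two paragraphs that should state one rule differ on the operative verb (*will* against *may*) and on the table that governs. Section 8.3 is not consistent within itself either: one sentence is unconditional, while the sentences around it recommend adjustments or make them conditional on need.

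This would be a drafting slip without consequence if every Table 1 hold were also a Table 4 reduction trigger, because both sections would then lead to the same dose. That is not the case, so for some holds the text leaves the resumption dose in doubt. A reduction lasts for the rest of treatment, so the answer after a first hold carries forward.

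Table 2 raises a separate question: at what toxicity grade may a subject restart after a grade 3 drug-related event?

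Subject safety and consistent dosing are at stake. Section 10.3 refers to investigational sites, Section 16.1 requires strict adherence to the protocol, and Section 11.4.1 requires deviations to be reported. Resuming at an unchanged dose after five days of grade 2 diarrhea could be logged as a deviation by a reader of Section 8.3 and accepted by a reader of Section 9.1.

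**Working it through.** The plan gives no figure to reproduce here. The check sets the tables side by side and takes the doses from Table 3.

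**Step 1: the table pointer.** Section 8.3 cites Table 1 for dose adjustments. Table 1 contains interruption criteria and no doses. The matching sentence in Section 9.1 cites Table 4, which does contain reductions. The pointer in Section 8.3 is therefore wrong on any reading.

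**Step 2: holds against reductions.** Each event is taken alone, with no other reaction of grade 3 or higher, and durations are in whole days.

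- Diarrhea: the Table 1 hold is grade 2 or higher "for more than 3 consecutive days despite supportive care", that is, from day 4. The Table 4 reduction needs grade 2 or higher for more than 7 consecutive days, that is, from day 8, or grade 3 or higher.
- Bleeding: the Table 1 hold is clinically significant bleeding of grade 3 or 4, or of grade 2 for 3 or more days. Table 4 has no bleeding row; its row for other reactions starts at grade 3.

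| Event | Hold (Table 1) | Reduction trigger (Table 4) | Reduction (8.3, read literally) |
|---|---|---|---|
| Grade 2 diarrhea, 1-3 days | no | no | does not arise |
| Grade 2 diarrhea, 4-7 days | **yes** | **no** | **yes** |
| Grade 2 diarrhea, 8 days or more | yes | yes | yes |
| Grade 2 bleeding, 3 days or more | **yes** | **no** | **yes** |
| Grade 3-4 bleeding | yes | yes | yes |

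The second and fourth rows show the mismatch. I do not count how many Table 1 criteria have such a gap. For the blood-pressure and platelet holds, that count would need CTCAE cut-offs that the documents do not give.

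**Step 3: the dose after a first such hold.** From Table 3, level 0 is 2 × 200 = 400 mg/day and level -1 is 2 × 150 = 300 mg/day.

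- Section 8.3 read literally: 300 mg/day, and 300/400 = 75% of the starting dose.
- Section 9.1 with Table 4: no dose stated. If silence is taken to mean the same dose, 400 mg/day (100%). No passage says this; it is an assumption.

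**Step 4: restart under Table 2.** Take another drug-related non-hematological event, with baseline grade 0.

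| Current grade | Heading allows restart | Fifth criterion allows restart |
|---|---|---|
| 0 or 1 | yes | yes |
| 2 | **no** | **yes** |
| 3 or higher | no | no |

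The two disagree at grade 2 only. The same holds for a baseline of grade 1.

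**The case against.** **Part 1 is a gap, not a contradiction.** The permissive verb in Section 9.1 can be read as permission to resume, since restart depends on Table 2, with the reduced dose taken as given. Silence in Table 4 does not contradict an express sentence in Section 8.3. This has force: always reducing the dose satisfies both sections. But Section 9.1 ties the reduction to Table 4, which omits two of the holds, and no passage says that the stricter instruction governs. The wrong pointer remains on either reading.

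**Section 8.3 is softer than one sentence suggests.** It refers the reader to Section 9, recommends adjustments according to individual tolerability, and makes the dose levels conditional on need. That is correct. It shows that the section is inconsistent within itself, and it does not cancel the unconditional sentence.

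**Table 2 largely answers itself.** The heading says that all criteria apply and names one exception, so the heading is the stricter when the two are applied together. This stands: for restart, the protocol does indicate how the criteria are to be read. The fifth criterion, as worded, still admits a grade that the heading excludes.

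**Oversight limits drift.** Section 10.1 provides for regular team review of drug administration, and Section 16.1 makes the Sponsor-Investigator responsible for overseeing treatment. Both help. Neither tells a treating physician which text to follow.

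**A stronger reading that does not hold.** A reader might infer that two sites could each comply fully and still give different doses. The documents do not support that: a site resuming at 400 mg/day after one of these holds departs from the unconditional sentence in Section 8.3, and a site restarting at grade 2 departs from the Table 2 heading.

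**Conclusion.** The inconsistency is real and can be seen in the current text. Section 8.3 has a wrong table pointer and differs from Section 9.1 on whether a hold leads to a reduction. For two kinds of grade 2 hold, Section 9.1 with Table 4 states no resumption dose. Table 2 gives restart thresholds one grade apart for other drug-related non-hematological events.

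The size is 300 mg/day under a literal Section 8.3, against an unstated dose under Section 9.1. The 400 mg/day comparator rests wholly on the assumption about silence. The examples assume that each event occurs alone.

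A reader might go on to infer a loss of relative dose intensity, a sequence of further reductions if such holds recur, or an effect on disease control. The documents support none of these as findings. The intended daily dose in Section 13.1.6 is not defined, recurrence only stacks more assumptions on the same silence, and nothing shows how many subjects would have these events. No effect on the primary endpoint, alpha or power is claimed.

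The correction should be made because the text directly sets dose and restart. Confidence is high for the differences in wording. How far actual dosing would diverge is unknown.

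**What to change.** Reconcile Sections 8.1, 8.2, 8.3 and 9.1:

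1. Make Sections 8.3 and 9.1 state one rule on the dose after a hold.
2. Correct the Table 1 pointer in Section 8.3.
3. State how Table 1 holds and Table 4 reductions relate for diarrhea and grade 2 bleeding, including the resumption dose where Table 4 is now silent.
4. Make the Table 2 heading and its fifth criterion agree.

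Which rule applies in each case is for the clinical team; this review takes no position.

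The cost is a protocol amendment and a memo to sites. Table 5 (Section 11.4.4) treats amendments as major changes, which need prior approval from both the IRB and the funding company. No visits or analyses are added.
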